9 CLINICAL MONITORING

9.1 Site Monitoring Plan

The Sponsor (or its designee) will monitor all aspects of the study, with respect to current Good Clinical Practices, and for compliance with applicable government regulations. Prior to the start of the study, the Principal Investigator will be informed of the frequency of monitoring visits and will be given reasonable notification prior to each visit. The objectives of a monitoring visit will be to verify the prompt reporting of SAEs, to check the availability of the signed Informed Consent and the child assent form for enrolled study subjects, to compare CRFs and spreadsheets with source data for completeness and accuracy, to verify compliance with the clinical protocol, and to check investigational product accountability. During the monitoring visit, the Principal Investigator (and/or designee) and other study personnel should be available to discuss the study. Study documents must be available for review throughout the course of the study.

10 STATISTICAL CONSIDERATIONS

10.1 Sample Size Considerations

This Phase 1 trial is not powered to detect statistically significant differences between groups. Even though comparative statistics for the safety variables will be computed, the study will have low power to detect anything other than very large differences in the incidence of local injection site and systemic side effects between the vaccination groups. This is done weighing the need to detect any possible untoward reactions against the need to limit the number of volunteers involved for safety purposes. The sample size of 60 for this study is within the range commonly used in Phase 1 trials for the initial assessment of the safety, tolerance and immunogenicity of investigational vaccines.

The primary objective of the study is to estimate the frequency of vaccine-related adverse events. Therefore, rather than providing a statistical power calculation for a specific hypothesis, we illustrate below the probability of observing one or more events, such as an adverse event of a particular type, for a single vaccine dose (N=20), formulation (N=30), or for all participants (N=60) under different assumptions of the true rate at which such events occur in the population.

	Probability of Observing 1 or More Events		
	N=20	N=30	N=60
"True" (but unknown) Probability of an Event			
0.5%	9.54%	13.96%	25.97%
1.0%	18.21%	26.03%	45.28%
3.0%	45.62%	59.90%	83.92%
5.0%	64.15%	78.54%	95.39%
10.0%	87.84%	95.76%	99.82%

As illustrated in the table above, the study will have high probability ($\geq 80\%$) of detecting events that are commonly occurring in the population. For example, with a sample of 20 participants (which is equivalent to the size of each dose group of Na-APR-1 (M74) in this study), there is an 87.84% probability of observing 1 or more events when the events occur at a rate of 10.0% in the population. As the sample size increases, the study is able to detect events that occur at lower rates. For example, using a sample size of 30 participants (which is equivalent to the number of participants assigned to vaccine co-administration in this study vs. Na-APR-1 (M74) alone), there is a 78.54% probability of observing 1 or more events that occur at a rate of 5% in the population. Using a sample of size 60 (equivalent to the entire study population) there is an 83.92% probability of observing 1 or more events that occur at a rate of 3% in the population. Detection of rare events—those that occur at a rate of 1% or less in the population—is not likely in this study.

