3 STUDY DESIGN

The study will be conducted as a randomized, placebo-controlled, double-blind Phase 1 dose-escalating clinical trial in healthy children between the ages of 6 and 10 years, inclusive, living in the hookworm-endemic area of Lambaréné, Gabon. The study is designed to evaluate the safety, reactogenicity, and immunogenicity of Na-GST-1/Alhydrogel® co-administered with Na-APR-1 (M74)/Alhydrogel®, as compared to the hepatitis B vaccine, in this age group.

Prior to beginning study-related activities, the consent and cooperation of representative community members will be sought, after which parents of potential pediatric participants will be invited to learn about the study and consent to the participation of their child. After a parent or legal representative provides written informed consent for the child's participation and passes the informed consent comprehension questionnaire, the child will undergo eligibility screening, including a complete medical history, physical examination, hematology testing, liver and renal function testing, HIV antibody testing, Hepatitis B and C serology, and urinalysis. In addition, a fecal examination will be performed for ova and parasites, and urine will be examined for *S. haematobium* ova. All clinically significant abnormalities will be reviewed with parents/legal guardians and referral of the child for follow-up care will be provided. After screening, those children determined to be eligible, based on the inclusion and exclusion criteria, will be invited to participate in the study.

Sixty children will be progressively enrolled into 1 of 3 Groups over a projected 3-month enrollment period, with each child followed for 9 months after the final injection (i.e., until Study Day 380 for those receiving vaccinations according to a 0,2,4-month schedule and until Study Day 448 for those receiving vaccinations according to a 0,2,6-month schedule). Group enrollment will be done in an open sequential fashion, whereas within each Group, investigational product (IP) assignment and vaccination will be done in a randomized double-blind fashion.

60 subjects will be enrolled into 3 groups of 20:

The first 20 subjects will be recruited and enrolled into Group 1:

- Group 1 double-blind IP allocation (n=20):
 - 16 subjects will receive 10µg Na-APR-1 (M74) plus 5µg GLA-AF delivered by IM injection in the deltoid muscle, with 10µg Na-GST-1 administered IM in the alternate arm.

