 - 8 will be vaccinated according to a 0,2,4-month schedule
 - 8 will be vaccinated according to a 0,2,6-month schedule
 - 4 subjects will receive hepatitis B vaccine comparator:
 - 2 will be vaccinated according to a 0,2,4-month schedule
 - 2 will be vaccinated according to a 0,2,6-month schedule
- Group 2 double-blind IP allocation (n=20):
 - 16 subjects will receive 30µg Na-APR-1 (M74) plus 5µg GLA-AF delivered by IM injection in the deltoid muscle, with 30µg Na-GST-1 administered IM in the alternate arm.
 - 8 will be vaccinated according to a 0,2,4-month schedule

- 8 will be vaccinated according to a 0,2,**6**-month schedule
- 4 subjects will receive hepatitis B vaccine comparator:
 - 2 will be vaccinated according to a 0,2,**4**-month schedule
 - 2 will be vaccinated according to a 0,2,**6**-month schedule
- **Group 3 double-blind IP allocation (n=20):**
 - 16 subjects will receive 100 μ g *Na-APR-1* (M74) plus 5 μ g GLA-AF delivered by IM injection in the deltoid muscle, with 100 μ g *Na-GST-1* administered IM in the alternate arm.
 - 8 will be vaccinated according to a 0,2,**4**-month schedule
 - 8 will be vaccinated according to a 0,2,**6**-month schedule
 - 4 subjects will receive hepatitis B vaccine comparator:
 - 2 will be vaccinated according to a 0,2,**4**-month schedule
 - 2 will be vaccinated according to a 0,2,**6**-month schedule

As with other aluminum hydroxide-adsorbed vaccines, hypersensitivity reactions would be expected to occur within the first 24 hours after receipt of either of the two vaccines, and other severe local or systemic reactions within 72 hours of vaccination. Children will therefore be observed for immediate reactions following each vaccination for at least 1 hour, and will have a clinical assessment either in their home or at the study clinic on Days 1, 3, 7, and 14 following each vaccination. See **Appendix A** for the schedule of clinical and laboratory evaluations.

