4.3.2 Allocation of vaccination schedule and vaccine randomization

Within each cohort the first 10 participants will receive the 0,2,4-month vaccination schedule and the last 10 will receive the 0,2,6-month schedule. The participants will be randomized to either the experimental group, receiving *Na-APR-1*(M74) plus 5 µg GLA-AF co-administered with *Na-GST-1*, or randomized to the control group who will receive HBV co-administered with sterile saline. In addition, there will be a randomization to assign left/right arm vaccination for the first injection, the arms will be alternated for the second and third sets of vaccinations. The Randomization list will thus only be used on Day 0 for a particular participant.

The vaccination manager assigns the Study ID when the vaccines are being prepared for that particular participant. The Study ID is written onto the syringes and then the vaccinator writes the Study ID onto the CRF.

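### The detection table in Section 10.1 counts hepatitis B comparators as hookworm vaccinees (20 for 16 per dose, 60 for 48 overall), and its N=30 column describes a contrast the trial does not contain

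*Combined protocol and SAP*

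**What the plan says.** Section 10.1 states the aim as follows: "The primary objective of the study is to estimate the frequency of vaccine-related adverse events". It gives no power calculation. Instead it tabulates the probability of at least one event at true rates of 0.5%, 1%, 3%, 5% and 10%, "for a single vaccine dose (N=20), formulation (N=30), or for all participants (N=60").

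The text below the table explains each column:

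- **N=20** is presented as the size of a dose group: "with a sample of 20 participants (which is equivalent to the size of each dose group of Na-APR-1 (M74) in this study". The example is 87.84% for a 10% event.
- **N=30** is said to be the "number of participants assigned to vaccine co-administration in this study vs. Na-APR-1 (M74) alone". The example is 78.54% for a 5% event.
- **N=60** is the whole study population: "there is an 83.92% probability of observing 1 or more events that occur at a rate of 3% in the population".

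Section 3 and the synopsis describe three groups of 20. In each, "16 subjects will receive" Na-APR-1 (M74) with GLA-AF in one arm and Na-GST-1 in the other, and "4 subjects will receive hepatitis B vaccine comparator". Section 4.3.2 confirms that controls receive hepatitis B vaccine with saline. On schedules it says: "Within each cohort the first 10 participants will receive the 0,2,4-month vaccination schedule and the last 10 will receive the 0,2,6-month schedule".

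**The concern.** A child who receives hepatitis B vaccine and saline cannot have an event caused by the hookworm vaccines. If the table is to show what the trial can reveal about those vaccines, its denominators should be the children who receive them. The N=20 description attributes an Na-APR-1 dose to 20 children when 16 receive it. The N=60 column is true to its label, but it includes 12 comparators. The N=30 description rests on a group given Na-APR-1 alone, and the trial has no such group.

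Section 10.1 otherwise supports the choice of 60 only by saying that it lies in the usual Phase 1 range. The table is therefore what a reader will use to judge what the absence of an event at a given dose means. Overstated probabilities make a clean dose level look more reassuring than it is.

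**Working it through.** **Inputs**

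- Hookworm vaccinees: 16 per group, 8 on each schedule (synopsis; Section 3). Total 3 × 16 = 48.
- Comparators: 4 per group, 2 on each schedule (same sections). Total 3 × 4 = 12, and 48 + 12 = 60.
- Per schedule: 3 × 8 = 24 vaccinees and 3 × 2 = 6 comparators, total 30.
- Children given Na-APR-1 alone: 0. Children given both antigens: 48.
- Event rates p: the five in the Section 10.1 table.

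**Formula.** P(at least one event) = 1 − (1 − p)^n.

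**Reproducing the plan.** With n = 20, 30 and 60, all 15 printed cells are recovered to two decimals. The three worked examples are:

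- 1 − 0.90^20 = 87.84%
- 1 − 0.95^30 = 78.54%
- 1 − 0.97^60 = 83.92%

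The formula is right. Only the choice and description of n are in question.

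**With vaccinees as the denominator**

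| True rate | Printed N=20 | n=16 | Printed N=60 | n=48 | Printed N=30 | n=24 |
|---|---|---|---|---|---|---|
| 0.5% | 9.54% | 7.71% | 25.97% | 21.38% | 13.96% | 11.33% |
| 1% | 18.21% | 14.85% | 45.28% | 38.27% | 26.03% | 21.43% |
| 3% | 45.62% | 38.57% | 83.92% | 76.82% | 59.90% | 51.86% |
| 5% | 64.15% | 55.99% | 95.39% | 91.47% | 78.54% | 70.80% |
| 10% | 87.84% | 81.47% | 99.82% | 99.36% | 95.76% | 92.02% |

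**Worked examples**

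- Per dose, 10% event: 1 − 0.90^16 = 81.47%, which is 87.84 − 81.47 = 6.37 points lower.
- All vaccinees, 3% event: 1 − 0.97^48 = 76.82%, which is 83.92 − 76.82 = 7.10 points lower.
- N=30, 5% event: read as described (children given co-administration), n is 48 and the value is 1 − 0.95^48 = 91.47%, so the printed 78.54% is too low. If the column was meant to be one schedule, the vaccinees number 24 and the value is 1 − 0.95^24 = 70.80%, so 78.54% is too high. The text does not define the column by schedule, so the second reading is a guess at its origin.

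**Event rate seen with 80% probability.** Solving for p gives 1 − 0.2^(1/n). This is 9.57% at n=16 against 7.73% at n=20, and 3.30% at n=48 against 2.65% at n=60. These rates are derived here and are not in the plan.

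**The case against.** The strongest counter-argument is that little here is an outright error and nothing depends on it.

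- **N=60 is labelled correctly.** It is the whole study population, and comparators also receive a vaccine. This stands. The figure is too high only for events related to the hookworm vaccines. That is nevertheless the natural reading, because the primary objective (Section 2.1) and outcome measures (Section 2.2.1) concern doses of the co-administered hookworm antigens.
- **Twenty is the operational unit.** The protocol uses the word group for the whole cohort of 20, halting rules count participants within a group (Section 8.5), and investigators are blinded within groups (Section 4.3.3). This supports keeping N=20 for blinded monitoring. It does not support calling 20 the number at a single vaccine dose.
- **Falling below 80% breaks no explicit promise.** The 80% statement concerns common events and is illustrated at 10%, and the printed 78.54% example is already below 80%. This also stands. The drop to 76.82% matters because it makes the example less favourable, not because it contradicts the text.
- **The conclusions survive.** Events at 10% remain likely to be seen at one dose (81.47%), and events at 1% remain unlikely to be seen even in all vaccinees (38.27%). This is correct and limits the severity.

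None of these points rescues the N=30 description.

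**Conclusion.** The concern holds. The N=20 and N=30 descriptions are wrong as written. The N=60 column is true to its label but too high for hookworm-vaccine-related events. In the plan's own examples the overstatement is 6.37 points (10% event, one dose) and 7.10 points (3% event, all vaccinees). The N=30 column has no matching set of children: it is understated if it means co-administered children and overstated if it means vaccinees on one schedule.

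The calculation assumes independent children with a common event rate, as the plan's table does, and full delivery of the allocation. Section 4.3.1 does not replace children who leave after the first vaccination, so 16 and 48 are upper limits for later doses.

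This should be fixed, but it does not undermine the design. No enrolment number, escalation step or halting rule takes the table as input.

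**What to change.** In Section 10.1:

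1. Replace the N=20 column with N=16 (7.71, 14.85, 38.57, 55.99, 81.47%), labelled as hookworm vaccinees at one dose.
2. Replace the N=60 column with N=48 (21.38, 38.27, 76.82, 91.47, 99.36%), labelled as all hookworm vaccinees.
3. Delete the N=30 column and its sentence, or redefine it as N=24 vaccinees on one schedule (11.33, 21.43, 51.86, 70.80, 92.02%).
4. Restate the worked examples as 81.47% (10% event, one dose) and 76.82% (3% event, all vaccinees).
5. If N=20 and N=60 are also kept for blinded group-level monitoring, label them as an event in any participant, comparators included.

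The cost is a table and wording change with no extra children or visits. The stated probabilities become slightly less favourable, and the 3% example drops below 80%. References to giving the antigens alone or separately also remain in Sections 10.2.1 and 10.3. They are a separate matter that this correction does not resolve.

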10.2 Planned Interim Analyses

See section 14.4 for timing of reports.

10.2.1 Safety Review

Descriptive and hypothesis-testing approaches will be used to estimate AE rates and to compare these rates in the different doses and formulations of Na-APR-1 (M74) alone or co-administered with Na-GST-1. Estimates will be presented with their 95% confidence intervals. Formal statistical tests, as outlined below, will be used to compare doses. No formal adjustments for multiple comparisons will be made. Statistical tests will use a two-sided significance level of 5%.

The proportion of subjects with at least one injection site AE will be compared by vaccine allocation (e.g., Na-APR-1 (M74) co-administered with Na-GST-1 vs. hepatitis B vaccine), by and by Na-APR-1 (M74)/Na-GST-1 dose.

Laboratory results (hematological and clinical chemistry) will be examined for trends over time and any clinically significant values for individuals will be reported.

10.2.2 Immunogenicity Review

The proportion of subjects with detectable anti-Na-GST-1 and anti-Na-APR-1 (M74) antibody responses, and the duration of these responses, will be summarized as descriptive measures. Geometric mean antibody responses will be compared between dose groups for each vaccine antigen with comparisons made by analysis of variance (ANOVA) tests and pair-wise comparisons by contrasts. Antibody responses will be measured at Days 0, 7, 14, 28, 56, 63, 70, 84, 112/180, 119/187, and 126/194 for interim analysis, with Days 140/208, 200/268, 290/358, and 380/448 added for final analysis.

To exploit the multiple measures of antibody within each subject, a longitudinal model may be built (if possible) to describe the antibody responses over time. The models will explore if there are any differences between those administered Na-APR-1 (M74)/Alhydrogel® co-administered Na-GST-1/Alhydrogel® and those administered the hepatitis B vaccine.

Summary statistics will be used to present exploratory study results of the cellular immune responses to Na-GST-1 and Na-APR-1 (M74) before and after immunization. To assess the changes in lymphocyte proliferative responses and cytokine/chemokine profiles over time, a generalized estimating equations model with robust standard errors will be constructed. When necessary, data reduction approaches will be used.

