2.2.4 Exploratory Outcome Measures

The following parameters will be evaluated for each dose of *Na-APR-1* (M74) co-administered with *Na-GST-1*:

1. Cellular immune response will be measured by a qualified indirect ELISA at approximately on days of vaccination, and then 7, 14, and 28 days after each vaccination, and approximately 3 and 6 months after the third dose.
2. Metabolomic profiles before vaccination, on days of vaccination, approximately 7 and 28 days following each vaccination, and 6 months after the third dose.

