10.3 Final Analysis Plan

The purpose of this trial is to estimate AE rates and patterns of immune response as well as to compare these rates and patterns when Na-GST-1/Alhydrogel® and Na-APR-1 (M74)/Alhydrogel® are administered separately or when they are co-administered.

This section briefly describes the statistical methods to be used; a detailed analytical plan will fully describe the methods. The analytical plan will discuss the planned approaches to missing data. Deviations from the original analytical plan will be thoroughly documented and reported to the Sponsor.

Descriptive and hypothesis-testing approaches will be used to meet the protocol objectives as stated in **Section 3**. Estimates will be presented with their 95% confidence intervals. Formal statistical tests, as outlined below, will be used to compare doses. Statistical tests will use a two-sided significance level of 5%.

Primary Objective: To evaluate the safety and reactogenicity of three different dose concentrations of *Na-APR-1* (M74)/Alhydrogel® co-administered with *Na-GST-1*/Alhydrogel® in healthy Gabonese children.

AEs will be coded according to Medical Dictionary of Regulatory Activities (MedDRA™) preferred terms. The frequency, severity, and relationship of AEs per each dose of *Na-APR-1* (M74)/Alhydrogel® and *Na-GST-1*/Alhydrogel® compared to Hepatitis B vaccine will be presented in tabular form using the MedDRA™ coded term and organized by MedDRA™ System, Organ, and Class (SOC) designations.

- The frequency of immediate, systemic, and local injection site AEs will be summarized by SOC and preferred term.
- Line listings of clinical and laboratory AEs classified as immediate (within the first 60 minutes), systemic, and local will be displayed in tables stratified by vaccine (i.e., hookworm vs. Hepatitis B vaccines) dose of *Na-APR-1* (M74)/Alhydrogel® and *Na-GST-1*/Alhydrogel®.
- AEs will be summarized by severity and relationship to vaccine by individuals and dose of *Na-GST-1* and *Na-APR-1* (M74).
- The frequency of vaccine-related SAEs will be tallied as well as summarized by body system, by vaccine and dose.

Primary Outcome Measures:

The following summary parameters will be evaluated for each vaccine (hookworm vs. Hepatitis B) and dose of *Na-APR-1* (M74) co-administered with *Na-GST-1*:

1. Frequency of solicited injection site and systemic reactogenicity, graded by severity, on the day of each study vaccination through 14 days after each study vaccination.

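### The exploratory GEE for cellular responses names no small-sample correction or reference distribution; with 12 to 16 children per group the standard version would exceed a nominal 5% level, modestly for single contrasts and severely for joint tests over all visits

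*Combined protocol and SAP*

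**What the plan says.** Section 10.2.2 (Immunogenicity Review, under the planned interim analyses) presents the cellular results as exploratory and mainly by summary statistics. For change over time it adds that "a generalized estimating equations model with robust standard errors will be constructed", with data reduction where needed. The working correlation, the coding of time, the hypothesis, the reference distribution and any small-sample correction are not stated.

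Section 10.3 states the error level: "Statistical tests will use a two-sided significance level of 5" per cent. Section 10.2.1 states the same level for the safety review. Section 10.2.2 does not repeat it. Section 10.3 also defers full methods to a detailed analytical plan. For the final cellular analysis it names only a longitudinal panel analysis of trends.

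Section 3 gives the sizes: "60 subjects will be enrolled into 3 groups of 20". In each group "16 subjects will receive" the hookworm antigens and "4 subjects will receive hepatitis B vaccine comparator". Each dose is split by schedule, so that "8 will be vaccinated according to a 0,2,4-month schedule" and 8 to the 0,2,6-month schedule.

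On visits, section 10.2.2 says "Antibody responses will be measured at Days 0, 7, 14, 28, 56, 63, 70, 84, 112/180, 119/187, and 126/194 for interim analysis"; that sentence concerns antibody. Section 2.2.4 sets the cellular measurements on vaccination days "and then 7, 14, and 28 days after each vaccination, and approximately 3 and 6 months after the third dose". Appendix A1 marks 14 cellular draws, 11 of them up to Day 126.

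**The concern.** Robust standard errors are justified by a large number of independent clusters. Each child is one cluster here, so a dose group supplies 16 and the pooled control group 12. With so few, the plain sandwich underestimates the variance, and a normal or chi-square reference ignores the uncertainty in that estimate. Both errors act in the same direction: p-values too small and intervals too short. The problem grows quickly with the number of time parameters tested together, because the covariance matrix of 10 visit differences is then estimated from 16 children or fewer.

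At stake are declared changes in proliferation, cytokines or chemokines that are not there. Section 7.2.2.5 intends the cellular and metabolic data to help explain neutralising antibody and possible adverse reactions, so spurious patterns could steer later mechanistic work.

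**Working it through.** **Is there a plan figure to reproduce?** The 5% is a declared level, not a derived one. The only calculated figures in section 10 are the 15 detection probabilities in 10.1. All 15 reproduce to two decimals, and they have no bearing on this point.

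**Inputs.**
- Section 3: 3 × 16 = 48 vaccinees, 3 × 4 = 12 controls, 60 in all.
- Appendix A1: 11 cellular draws up to Day 126. On Days 7, 63 and 119 the daily blood volume is 2.5 mL, which cannot hold the 5 mL cellular sample. If those draws are not made, 8 remain.
- Assumptions, because the documents are silent: complete data, plain sandwich, normal or chi-square reference. For joint tests, each visit is a category.

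**Within one group (exact for normal data).** With a saturated time model and complete data, GEE returns the visit means, and the sandwich is the sample covariance with divisor n. For n children and q degrees of freedom, the Wald statistic W satisfies W(n − q)/(nq) ~ F(q, n − q). The true size at a nominal 5% is therefore

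P{ F(q, n − q) > χ²(0.95, q) × (n − q)/(nq) }.

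| n | q | χ² critical value | F threshold | True size |
|---|---|---|---|---|
| 16 | 1 | 3.841 | 3.841 × 15/16 = 3.601 | 7.7% |
| 12 | 1 | 3.841 | 3.841 × 11/12 = 3.521 | 8.7% |
| 60 | 10 | 18.307 | 18.307 × 50/600 = 1.526 | 15.8% |
| 16 | 10 | 18.307 | 18.307 × 6/160 = 0.687 | 71.5% |
| 60 | 7 (8 draws) | 14.067 | 14.067 × 53/420 = 1.775 | 11.2% |
| 16 | 7 (8 draws) | 14.067 | 14.067 × 9/112 = 1.130 | 42.2% |

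The n = 60 rows treat all children as one group. With separate means for the three doses and controls, the pooled 10-df time test simulates at 19%.

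**Between groups (simulation under the null; normal data, exchangeable correlation 0.5).**
- Single contrast or slope, 1 df: 16 v 16 about 6.6–7.1%; 16 v 12 about 7%; 48 v 12 about 8%. Skewed (lognormal) data, 16 v 12: 6.2%. For comparison, a linear trend within one group gives 8.2% at n = 16 and 9.1% at n = 12.
- Joint group-by-time over 11 draws, 10 df: 16 v 16 34%; 16 v 12 43%; all 48 vaccinees v 12 controls 51%. Four groups, 30 df: 90%.
- Joint over 8 draws: 16 v 12 about 26%; four groups 61%.
- Robustness of the 43%: 42% with AR(1) correlation 0.8, and 41% with lognormal data.
- A standard GEE fit (exchangeable working correlation, 1,500 runs, 16 v 12) gave 7.3% and 7.7% for two 1-df tests and 43% for the joint test.

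**By schedule.** If a model were fitted within one dose-by-schedule cell, n = 8: a 1-df test runs at 10.9%, and the 10-df sandwich cannot be inverted.

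**Interval width.** The ratio of the plain interval to the t interval is √((n − 1)/n) × 1.960/t(0.975, n − 1).
- n = 16: 0.968 × 1.960/2.131 = 0.890, about 11% too narrow.
- n = 60: 0.992 × 1.960/2.001 = 0.971, about 3% too narrow.

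**Does the remedy work?** For 16 v 12 and 11 visits (1,500 runs), a Mancl-DeRouen sandwich with t or F reference gives 3.8% for a single contrast, 5.3% for a slope difference and 4.8% for the joint 10-df test. The same corrected sandwich with a chi-square reference still gives 32.8% for the joint test, so both parts are needed.

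**The case against.** A reader might infer that the plan commits to uncorrected standard errors and that every cellular test will run far above 5%. The documents do not support that reading.

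- No text says that the sandwich is uncorrected. The correction is simply not mentioned, and section 10.3 leaves full methods to an analytical plan.
- No joint test over visits is promised. The final analysis speaks of trends over time, which fits a low-df test at least as well, and data reduction is allowed. The 72% also needs a separate model within one dose group.
- Section 10.2.2 states no significance level for the GEE, and section 10.3, which does, does not name the GEE.
- The 11 days listed in 10.2.2 are antibody days. The cellular count has to be taken from Appendix A, where the blood volumes leave open whether it is 11 or 8.
- The results are exploratory. Section 14.4 bases the interim report on safety and antigen-specific IgG data, and section 10.3 already plans a Mann-Whitney comparison of cytokine levels two weeks after the final vaccination, which sandwich bias does not touch.

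All of this stands, and it limits the point to an omission in an exploratory analysis. It does not remove the omission. The estimator is named without the details that decide whether it is valid at this size, and the standard version exceeded 5% in every case tried. Three vaccinations make a straight line a doubtful description of the response, so categorical time is a natural choice for an analyst to make.

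**Conclusion.** The plan names a robust GEE for the exploratory cellular responses and leaves out the small-sample correction and the reference distribution. If the standard form is used, the excess over a nominal 5% is modest for single contrasts or linear trends (about 6–9%).

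It is severe only if visits are categories tested jointly. Over 11 draws the rates are about 16% pooled, 34–43% for one dose group against another or against controls, 72% within one dose group and 90% for four groups by time. Over 8 draws they are about 11% pooled, 26% for 16 v 12 and 42% within one dose group.

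Pointwise intervals would be about 11% too narrow at n = 16 and 3% at n = 60. These figures assume complete data, and children who leave are not replaced, so losses would push them slightly higher. No primary or secondary conclusion is affected.

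**What to change.** In the analytical plan, keep GEE and specify:

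1. A bias-corrected sandwich (Mancl-DeRouen or Kauermann-Carroll) together with a t or F reference. The correction alone is not enough for multi-df tests.
2. The coding of time, and a short list of prespecified contrasts, with Day 0 to 14 days after the third dose first, in place of a joint test over all visits.
3. The cellular visits that enter the model, once the 2.5 mL draw days in Appendix A are reconciled with the 5 mL sample.

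A mixed model with Kenward-Roger degrees of freedom is a possible alternative, but not clearly better. Cytokine data are often skewed, and an unstructured covariance over 11 visits has 11 × 12/2 = 66 parameters for 60 children. If no inference is intended, the plan should say that the model is descriptive only.

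The cost is wording and standard software, with no added children, visits or blood. The downside is somewhat wider intervals.
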